10.2.2 Screening (Enrollment and Baseline)

Because patients are enrolled after a snakebite with envenoming, each subject must be screened, and treated within the first day (Day 1) of the study. Following completion of all assessments and confirmation of eligibility, the subject will be randomized via the IWRS.

The following critical assessments/procedures must be performed at enrollment, prior to initiation of IP treatment: informed consent, inclusion/exclusion criteria review, medical history, physical examination, vital signs, SSS, Head-Lift, NPRS, and pre-dose laboratory blood draws. The following noncritical assessments should be performed as early as possible, but may be performed after randomization and initiation of study drug and SOC if required due to patient condition: demographic information, height/body weight, 12-lead ECG, grip strength, PGIC, CGI-I, and C-SSRS.

The following procedures will be performed at Screening:

Baseline:

- Obtain informed consent, either from the subject or a legally authorized representative
- Review inclusion/exclusion criteria
- Record prehospital tourniquet use as a snakebite treatment
- Record hospitalization details
- Record pulmonary support interventions
- Perform physical examination
- Measure vital signs per institutional practice
- Perform individual assessments pertaining to the SSS (A scoring sheet for use by study personnel is provided in Appendix A; clinical evaluation of the overall SSS [Appendix B] will be performed after completion of the study):
 - i. Local wound severity
 - ii. Pulmonary severity
 - iii. Cardiovascular severity
 - iv. Gastrointestinal severity
 - v. Hematologic severity (do not wait for laboratory results)
 - vi. Renal severity (do not wait for laboratory results)
 - vii. Nervous system severity
- Measure Head-Lift duration (0 to 5 seconds)
- Perform NPRS
- Collect blood and urine for the following laboratory assessments:
 - i. CBC

Ophirex, Inc.

Confidential

OPX-PR-01

- ii. Serum chemistry
- iii. CK
- iv. LFTs
- v. eGFR
- vi. Hemolysis (Free hemoglobin, haptoglobin, lactate dehydrogenase [LDH])
- vii. Prothrombin time (PT), partial thromboplastin time (PTT), thrombin time, INR
- viii. Absolute fibrinogen
 - ix. Urinalysis
 - x. sPLA₂ (see Section 10.2.1)
- xi. Urine pregnancy
- xii. Serum pregnancy test (subjects of childbearing potential only)
- xiii. Biomarkers (C-reactive protein [CRP], and D-dimer)

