## 8.2. Other Secondary Efficacy Analyses

The other secondary efficacy analyses will be interpreted as exploratory analyses. All secondary endpoints will be analyzed according to the prespecified assessment timepoints listed in the protocol. Statistical models will include covariates for baseline SSS, baseline neurotoxicity (Yes, No; based on the SSS neurological system subscore), age group (5-17, 18+), and, when available, the baseline value of the particular endpoint unless otherwise specified below. A sensitivity analysis will include as a covariate yes/no completion of an initial dose of antivenom prior to randomization. The methods described here are what is currently planned. However, for each analysis, we will examine the distribution of the strata pooled over treatment and placebo. If the data are unlikely to support the planned analysis or if the model fails to converge, removal of covariates and different estimation routines will be attempted and described in the CSR.

### 8.2.1. Complete SSS from Baseline through Day 7

The complete SSS (all sub-sections including pulmonary, cardiovascular, hematologic, renal, nervous system, gastrointestinal, and local wound) from baseline through Day 7 after first dose will be summarized using descriptive statistics of observed values and changes from baseline.

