The post baseline complete SSS scores at each time point will be analyzed, without replacement of missing values, using a restricted maximum likelihood (REML) based repeated measures approach (MMRM). Analyses will include a random intercept and the fixed effects of treatment, baseline total SSS, age group (5-17 years,  $\geq$  18 years), baseline neurotoxicity, and visit (categorical) as covariates. The model will include a treatment-by-time interaction. An unstructured covariance model will be used to model the within-subject errors. The Kenward-Roger approximation will be used to estimate denominator degrees of freedom. If this analysis fails to converge, simpler structures (e.g., first-order compound symmetry and then autoregressive order-1 structures) will be tested in a model without treatment effect; the covariance structure and the degree of freedom approximation converging to the best fit, as determined by Akaike's Information Criterion, will be used in the full model. A description of all tested models and results from these models will be provided as an appendix in the CSR. Within this model, the estimate of interest is the effect of treatment at each time point, performed at significance level of 5%. The corresponding 95% two-sided confidence intervals will be presented at each time point of assessment.

### 8.2.2. SSS Neurologic System Subscore from Baseline through Day 3

The SSS neurologic system subscore from baseline through Day 3 after first dose will be summarized using descriptive statistics of observed values and changes from baseline. The SSS neurologic system subscore will be analyzed with a similar MMRM as the one described in [Section 8.2.1](#). The MMRM will be used to assess the treatment effect on change in SSS neurologic system subscore through Day 3. The MMRM will include treatment as fixed effect as the variable of interest, with visit and visit by treatment interaction as covariates. The model will be used to estimate the effect of treatment on SSS neurologic subscore at each assessment time

point through Day 3. Treatment effect will be summarized via LS means, p-values, and 95% two-sided confidence intervals.

This analysis will be conducted in two groups of patients: (1) subjects with a baseline SSS neurologic system subscore  $\geq 1$ ; and (2) subjects with a baseline SSS neurologic system subscore  $\geq 2$ .

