Note: The effect of varespladib on neurotoxicity is supported by the observation that varespladib prevents, reverses, or delays lethality from venom neurotoxicity in animals experimentally envenomed with Mojave rattlesnake, coral snake, krait, and taipan venoms even when administered at a point when weakness is refractory to antivenom reversal (e.g., Prasarnpun 2005; Anil et al. 2010; Lewin et al. 2018a, 2018b; and Gutierrez et al. 2021). Neurologic outcomes were not selected as the focus of the primary or key secondary efficacy endpoints because of the unexpectedly small number of severely neurotoxic patients enrolled in the trial.

### 8.2.3. Coagulation Abnormalities from Baseline through Day 7

Each of the four coagulation lab values (PT, PTT, platelets, and fibrinogen) will be analyzed using a proportional odds logistic regression with five ordered categories. Categories for the lab values in each of these analyses will use those defined by the Snakebite Severity Score (Dart et al. 1996), with normal lab values receiving a score of 0 and abnormal lab values receiving a score of 1 to 4 based on the following published cutoffs.

Coagulation Parameter	0	1	2	3	4	Units
Prothrombin Time	Lab validated reference range	Above lab ref range to 20 sec	>20 to 50 sec	>50 to 100 sec	Unmeasureable or above 100 sec	Sec
Partial Thromboplastin Time	Lab validated reference range	Above lab ref range to 50 sec	>50 to 75 sec	>75 to 100 sec	Unmeasureable or above 100 sec	Sec
Platelet count	Lab validated reference range	100,000 to ref	50,000 to <100,000K	20,000 to <50,000	Less than 20,000	/mL
Fibrinogen	Lab validated reference range	100 to ref	50 to <100	Less than 50	Undetectable	mg/dL

Analysis for each of the four coagulation parameters will be run separately for each time point from Day 1 3 hours to Day 7. The models will use the following covariates: baseline SSS score, age group (5 to 17 years,  $\geq$  18 years), baseline neurotoxicity, receipt of antivenom prior to baseline (Yes, No), and country. The treatment effect will be summarized with an estimated odds ratio and tested at a 5% two-sided significance level; the corresponding 95% two-sided confidence intervals will be presented. These analysis will only include subjects with lab value-specific coagulation abnormalities (hematology subscore  $\geq$  1 as derived from the relevant coagulation lab value) at baseline.

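### The coagulation models in SAP 8.2.3 list their covariates without the baseline category of the laboratory value being modelled

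*SAP*

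**What the plan says.** SAP 8.2 sets the default for the other secondary models: baseline SSS, baseline neurotoxicity, age group, "and, when available, the baseline value of the particular endpoint unless otherwise specified below".

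SAP 8.2.3 then describes the coagulation analysis. Each of the four laboratory values is "analyzed using a proportional odds logistic regression with five ordered categories", in a separate model at each time point. On covariates it says "The models will use the following covariates: baseline SSS score, age group", and the list ends with "baseline neurotoxicity, receipt of antivenom prior to baseline (Yes, No), and country". On the analysis set it says "These analysis will only include subjects with lab value-specific coagulation abnormalities", meaning a category of at least 1 at baseline on the parameter concerned.

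The baseline values exist. Protocol 10.2.2 lists "Prothrombin time (PT), partial thromboplastin time (PTT), thrombin time, INR" among the pre-dose draws, together with fibrinogen and the CBC that contains the platelet count.

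**The concern.** A patient who starts in category 4 and one who starts in category 1 have different prospects of being normal a few hours or days later, whatever the treatment. If the model ignores where each patient started, that variation stays in the noise. In a proportional-odds model it also pulls the estimated treatment odds ratio toward 1. Randomisation is stratified by age and neurotoxicity, not by coagulation status, so a chance imbalance in starting category within one of these subsets would be corrected only through the composite score.

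The scale of use is not trivial. Four parameters at six post-dose assessments through Day 7 (3-4 h, 5-6 h, 8-10 h, Days 2, 3 and 7) make 4 x 6 = 24 fits, each tested at 5%. The SAP should leave no doubt about which model is fitted.

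**Working it through.** **1. Does the 8.2.3 list replace the 8.2 default?**

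| Covariate | 8.2 default | 8.2.3 coagulation | 8.1.2.2 antivenom |
|---|---|---|---|
| Baseline SSS | yes | yes | yes |
| Baseline neurotoxicity | yes | yes | yes |
| Age group | yes | yes | yes |
| Endpoint's own baseline | when available | not named | not named |
| Prior antivenom | sensitivity analysis only | yes | yes |
| Country | no | yes | yes |

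The 8.2.3 list repeats three of the four default items, adds two, and leaves out only the fourth. A list meant as a supplement would not need to repeat the other three. It matches the antivenom model in 8.1.2.2 item for item, and the sample code for that model in 8.1.3 contains exactly those terms. Antivenom is counted only after study drug (6.1.7.7), so it has no baseline of its own; a laboratory category does.

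Other sections name their own baseline: 8.2.4 (free hemoglobin), 8.2.5 (CK), 8.2.6 (NPRS), 8.2.7 (kidney function), 8.2.8 (head-lift), 8.2.13 (CGI-I) and 8.2.14 (PGI-C). PSFS in 8.2.15 does not, but the schedule has no baseline PSFS.

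**2. Does another rule fill the gap?** The rule in 8.1.2 covers models for change from baseline, and the baseline-by-time term in 6.1.2 belongs to the MMRM. An ordinal model of the category at one time point is neither.

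**3. How much does baseline SSS already carry?** It sums five sections (6.1.2) with a maximum of 3 + 3 + 4 + 3 + 3 = 16. The hematologic section contributes at most 4 and pools the four laboratory values into one score. It is a partial proxy.

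**4. The plan's own figure.** The only power statement concerns the primary endpoint: 94 evaluable for a difference of 1.1 with SD 1.75. It reproduces: 47 per arm gives 85.4% by the noncentral t. It does not bear on these models, for which no power is stated.

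**5. Size, linear approximation (assumed inputs).** Let rho be the correlation of own baseline with outcome and r that of own baseline with the proxy, the proxy predicting only through baseline. The standard-error ratio is sqrt[(1 - rho^2)/(1 - (rho r)^2)]. For r from 0 to 0.7:
- rho = 0.3: ratio 0.954 to 0.976, a reduction of 2.4 to 4.6%.
- rho = 0.5: ratio 0.866 to 0.925, a reduction of 7.5 to 13.4%.
- rho = 0.7: ratio 0.714 to 0.819, a reduction of 18.1 to 28.6%.

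**6. Size, proportional odds (assumed inputs).** 250 simulated trials per row; true odds ratio 3 (log 1.10); baseline categories 1 to 4 at 40/25/15/20%; treatment plus one proxy covariate, with or without the own-baseline category as a linear term. Power is in %; log OR is the median estimate, without / with.

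| OR per baseline category | N | r | Without | With | Gain | Log OR |
|---|---|---|---|---|---|---|
| 1.65 | 40 | 0.3 | 35.6 | 36.4 | 0.8 | 1.03 / 1.10 |
| 1.65 | 40 | 0.6 | 40.8 | 47.2 | 6.4 | 1.15 / 1.26 |
| 1.65 | 60 | 0.3 | 52.4 | 59.6 | 7.2 | 1.05 / 1.18 |
| 1.65 | 60 | 0.6 | 56.8 | 60.4 | 3.6 | 1.06 / 1.17 |
| 2.72 | 40 | 0.3 | 29.6 | 42.4 | 12.8 | 0.98 / 1.20 |
| 2.72 | 40 | 0.6 | 37.6 | 44.4 | 6.8 | 1.05 / 1.28 |
| 2.72 | 60 | 0.3 | 42.4 | 54.0 | 11.6 | 0.87 / 1.13 |
| 2.72 | 60 | 0.6 | 44.8 | 53.6 | 8.8 | 0.96 / 1.10 |
| 4.48 | 40 | 0.3 | 22.4 | 40.0 | 17.6 | 0.77 / 1.22 |
| 4.48 | 40 | 0.6 | 22.4 | 38.0 | 15.6 | 0.87 / 1.21 |
| 4.48 | 60 | 0.3 | 33.2 | 50.0 | 16.8 | 0.71 / 1.17 |
| 4.48 | 60 | 0.6 | 33.6 | 53.6 | 20.0 | 0.84 / 1.20 |

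Each power has a simulation error of about sqrt(0.5 x 0.5/250) = 3 points.

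A second simulation used all five listed covariates, odds ratio 3.3, composite-to-laboratory correlation 0.5 and 200 replicates (error about 3.5 points). Power without and with the baseline category was:
- N = 50, baseline correlation 0.3: 50.5% and 51.0%.
- N = 50, correlation 0.6: 36% and 49.5%.
- N = 25, correlation 0.5: 26% and 30.5%.
- N = 50, correlation 0.3, with 75% of controls in category 0: 15% and 17%, about a third of fits being unstable under either model.

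**The case against.** The strongest reply is that 8.2.3 never says its list is exhaustive. Read together with 8.2, the own baseline could still be in the model, which makes this an ambiguity and not a decision. That stands as far as it goes. But the default applies "the baseline value of the particular endpoint unless otherwise specified below", a specific list is the usual way of specifying otherwise, and a programmer adapting the antivenom code would leave the term out.

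It is also fair that baseline SSS includes the hematologic section, that restriction to category 1 or above removes some baseline variation, and that sparse outcomes may not support another term. These points reduce the gain in some settings; they are not a reason to leave the model unclear.

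Three stronger readings are tempting and not supported:

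- A reader might infer the same gap in the neurologic-subscore model, because 8.2.2 says "The MMRM will include treatment as fixed effect as the variable of interest, with visit and visit by treatment interaction as covariates". That sentence cannot be the whole model, since it also omits age group and baseline SSS. Section 8.2.2 calls the model similar to 8.2.1, which adjusts for its own endpoint's baseline. The defaults in 8.2, the baseline-by-time term in 6.1.2 and the change-from-baseline rule in 8.1.2 point the same way.
- A reader might say the plan throws away its strongest predictor. The documents give no baseline-outcome correlation, and part of the information enters through baseline SSS.
- A reader might quote one gain. With 50 patients, odds ratio 3.3, baseline-outcome correlation 0.5 to 0.7 and composite correlation 0.4 to 0.6, it is 9 to 13 points. That is one region of a range that starts near zero.

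**Conclusion.** The point holds for coagulation. As most naturally read, 8.2.3 fits its models without the baseline category of the parameter being modelled, although that category is known for every analysed subject and can take four values.

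The size is uncertain because it rests on a subset size and a baseline-outcome association that the documents do not give. It is roughly 0 to 8 power points if baseline is weakly prognostic, 7 to 13 at the intermediate setting, and about 16 to 20 if strongly prognostic. At the strong end the median log odds ratio without the term is 0.71 to 0.87 against a true 1.10, an odds ratio of about 2.0 to 2.4 in place of 3.

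This attenuation is non-collapsibility: the two models estimate different odds ratios, and the unadjusted one is not thereby invalid. Randomisation keeps the test valid. SAP 8.2 classes these analyses as exploratory, and they lie outside the fixed testing sequence. The primary and key secondary tests, the sample size and type I error are untouched. It is a worthwhile low-cost improvement, not a threat to the trial's conclusions.

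**What to change.** In SAP 8.2.3, add to each model the baseline category of the same laboratory value (1 to 4, as a linear term, one degree of freedom), and say that the odds ratio is conditional on it. Allow it to be dropped only under the existing 8.2 provision for data that will not support the model or fits that fail to converge, with each instance reported in the CSR.

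The cost is one sentence in the SAP and one degree of freedom per model, with no new data. It should be settled before unblinding; after that, SAP 1 would require it to be identified as post hoc.

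Naming the baseline neurologic subscore in 8.2.2 would be a useful clarification, but no more than that.

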#### **8.2.4. Hemolysis Markers at Baseline through Day 3**

Concentrations of free hemoglobin through Day 3 will be presented using graphs and summary statistics by treatment arm and time points.

An MMRM approach as described in [Section 8.2.1](#) will be used to assess the treatment effect on change in free hemoglobin (continuous variable) through Day 3. The MMRM will include treatment as fixed effect, baseline SSS, age group, baseline free hemoglobin, baseline neurotoxicity, visit, and visit by treatment interaction as covariates. The model will be used to estimate the effect of treatment on hemolysis at each assessment time point through Day 3. Treatment effect will be summarized by LS means, p-values, and 95% two-sided confidence intervals.

Only subjects with hemolysis at baseline (free hemoglobin  $\geq$  15 mg/dL) will be included in this analysis. Additional analyses will examine the effect of treatment on other indicators of hemolysis including LDH and haptoglobin.

#### **8.2.5. Levels of the Myonecrosis Marker (CK) from Baseline Through Day 3**

Absolute value and change from baseline of creatine kinase (U/L) will be presented in graphs and summarized descriptively by treatment at baseline through Day 3.

An MMRM approach as described in [Section 8.2.1](#) will be used to assess the effect of treatment on change in CK through Day 3. The MMRM will include treatment as a fixed effect as the variable of interest, with baseline CK, baseline neurotoxicity, age group, visit, and visit by treatment interaction as covariates. The model will be used to estimate the effect of treatment on myonecrosis at each assessment time point through Day 3. Treatment effect will be summarized by LS means, p-values, and 95% two-sided confidence intervals.

Only subjects with CK  $\geq$  2x institutional reference range at baseline will be included in this analysis.

#### **8.2.6. NPRS Score in Subjects Able to Respond from Baseline through Day 28**

The absolute values and change of NPRS will be tabulated by treatment arm and visit. An MMRM approach as described in [Section 8.2.1](#) will be used to assess the treatment effect on NPRS scores through Day 28. The MMRM will include the fixed effect of treatment as the variable of interest, with the baseline NPRS, baseline SSS, age group, baseline neurotoxicity, and visit, and visit by treatment interaction as covariates.

#### **8.2.7. Kidney Function Markers from Baseline through Day 28**

Descriptive summaries of absolute value and change from the baseline of kidney function markers (i.e., creatinine) will be tabulated by treatment group and visit. The mean change from baseline through Day 28 will be compared between treatment arm using an MMRM. The MMRM will include treatment as fixed effect as the variable of interest, with the baseline SSS, baseline kidney function measure, age group, baseline neurotoxicity, and visit, and visit by treatment interaction as covariates. The model will be used to estimate the effect of treatment on kidney function at each assessment time point through Day 28. Treatment effect will be summarized by LS means, p-values, and 95% two-sided confidence intervals.

Only subjects with a creatinine  $\geq 2x$  the upper limit of normal at baseline will be included in the analysis.

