8.2.2 Exclusion Criteria

A subject will be excluded from the study if he or she meets any of the following criteria:

OPX-PR-01

1. Is considered by the Investigator to have a clinically significant upper GI bleed evidenced by significant hematemesis, "coffee-ground" emesis or nasogastric aspirate, hematochezia thought to originate from upper GI tract.

- 2. Has history of CVA or intracranial bleeding of any kind, acute coronary syndrome, MI, or severe pulmonary hypertension.
- 3. Has known history of inherited bleeding or coagulation disorder.
- 4. Is, at Screening Visit, using the following anticoagulants: warfarin/coumadin, argatroban, bilvalirudin, lepirudin, apixaban, dabigatran, clopidogrel, prasugrel, ticlodipine or another anticoagulant agent not specifically listed, or has used heparin, enoxaparin, fondaparinux, or other low molecular weight heparin or antiarrhythmic drugs within 14 days prior to treatment.
- 5. Has a history of chronic liver disease such as chronic active viral hepatitis, alcohol-related liver disease, non-alcoholic steatohepatitis, non-alcoholic fatty liver disease, hemochromatosis, primary biliary cirrhosis, primary sclerosing cholangitis, autoimmune hepatitis.
- 6. Reports or has known pre-existing renal impairment or chronic kidney disease.
- 7. Has a known allergy or significant adverse reaction to varespladib-methyl.
- 8. Is considered by the Investigator to be unable to comply with protocol requirements due to geographic considerations, psychiatric disorders, or other compliance concerns.
- 9. Is pregnant, has a positive serum human chorionic gonadotropin (hCG) pregnancy test or not willing to use a highly effective method of contraception for 14 days after initial treatment, or is breast-feeding.

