Analysis of the secondary endpoints will be carried out for the ITT population.

All secondary endpoints will be summarized using frequencies and percentages for categorical endpoints, and numeric summary statistics for quantitative endpoints.

Additional ANCOVA or a repeated measures model (MMRM) analyses will be considered for quantitative secondary endpoints.

All-cause mortality will be analyzed using Kaplan-Meier methods.

PGI-C and CGI-I responders will be summarized by frequency and percentage at each visit within treatment group. The difference in treatment response will be analyzed using a logistic regression model at each visit with baseline SSS score, age group (5 to < 18 and \geq 18 years), neurological system subscore \geq 2 (Yes or No), and completion of the initial dose of antivenom prior to initiation of study drug (Yes or No) as covariates.

Additional details of the efficacy analyses will be given in the final SAP.

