#### **3.2. Sample Size and Power**

The sample size for this phase 2 study was determined by a formal power calculation based on the primary efficacy endpoint. This study was powered at 85% to detect a statistically significant (2-sided alpha = 0.05) treatment effect. The assumptions are the following:

- 2-sided alpha level 5%
- Power 85%
- Randomization ratio 1:1
- A minimum difference in the change from Baseline to the average at 6- and 9-hour pulmonary, cardiovascular, hematologic, renal, and nervous system subscores of the SSS of 1.1 points and a standard deviation 1.75

A sample size of 94 patients will provide 85% power to identify a difference of 1.1 in the primary outcome (two-sided alpha = 0.05). The sample size has been calculated using nQuery 8.

The randomization scheme will be 1:1 stratified by age group (5 to < 11, 11 to < 18, and  $\geq$  18 years old) and by the presence or absence of neurotoxicity (SSS nervous system subscore of 0–1 or  $\geq$  2) at Baseline, resulting in 6 strata in total.

Because we anticipate up to 15% withdrawal through the end of the study, we requested permission to enroll up to 110 patients to ensure adequate power for secondary outcomes.

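### The SAP limits the kidney, CK, hemolysis and coagulation models to patients already abnormal at baseline, contrary to the stated ITT population, so these marker-specific analyses cannot test prevention of new injury

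*SAP*

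**What the plan says.** Protocol 13.1.4.5 (Secondary Analyses) sets the population: "Analysis of the secondary endpoints will be carried out for the ITT population". SAP section 5 assigns ITT to all efficacy analyses, and SAP 8.1.2 repeats it for the secondary endpoints. The marker sections of the SAP then narrow it:

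- **Kidney (8.2.7):** creatinine at least twice "the upper limit of normal at baseline will be included in the analysis".
- **CK (8.2.5, repeated by tourniquet status in 8.3.12):** CK at or above "2x institutional reference range at baseline will be included in this analysis".
- **Hemolysis (8.2.4):** "Only subjects with hemolysis at baseline", defined as free hemoglobin of 15 mg/dL or more. LDH and haptoglobin are to be examined as well, but neither method nor population is given for them.
- **Coagulation (8.2.3):** "These analysis will only include subjects with lab value-specific coagulation abnormalities", judged separately for PT, PTT, platelets and fibrinogen.

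In the table list (SAP 13.2), the CK, hemolysis and coagulation model titles name their subset. The kidney title (Table 14.2.9.1) says ITT Population and names none. SAP section 10 (Changes from Planned Analysis) does not mention the restrictions.

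SAP 8.2 states that all these analyses are exploratory. They lie outside the fixed testing sequence.

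**The concern.** Protocol 5.1.1 attributes hemolysis, coagulopathy, myonecrosis and kidney damage to venom sPLA2. An inhibitor given early could act by preventing such injury as well as by speeding its resolution. A model confined to patients already abnormal before dosing can address only resolution. A patient with normal creatinine at hour 0 and renal failure on Day 3 is outside the kidney model. A patient whose CK rises on Day 2 from a normal baseline is outside the CK model.

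The kidney restriction may also leave few patients. Protocol 8.2.2 excludes a patient who "Reports or has known pre-existing renal impairment or chronic kidney disease". Protocol 8.2.1 requires symptom onset within 10 hours of eligibility assessment and does not count the renal score towards entry. Protocol 8.4 provides for withdrawing enrolled patients whose renal tests suggest they meet an exclusion criterion. A reader of the kidney table, seeing only ITT in its title, could take a result from a handful of patients for one from all randomized patients.

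**Working it through.** **1. The plan's own figure.** SAP 3.2 gives "2-sided alpha level 5" percent, 1:1 allocation, a difference of 1.1 and an SD of 1.75, and states: "A sample size of 94 patients will provide 85% power to identify a difference of 1.1 in the primary outcome".

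- Normal approximation: n per arm = 2(1.960 + 1.036)² × (1.75/1.1)² ≈ 45.4, so 46 per arm and 92 in total.
- Noncentral t: 47 per arm, 94 in total, power 85.4%. The stated figure reproduces.
- Enrolment: 94/0.85 = 110.6 against 110 stated.

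Neither document gives a sample size, power or expected count for any baseline-abnormal subset.

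**2. Size of the kidney subset.** Let f be the share of patients with baseline creatinine at least twice the upper limit of normal. The documents give no f, so every row is an assumption. The count follows a binomial distribution with N = 110.

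| Assumed f | Expected patients (110f) | P(fewer than 5) | P(8 or fewer) |
|---|---|---|---|
| 2% | 2.2 | 93% | >99% |
| 5% | 5.5 | 35% | 90% |
| 10% | 11 | 1% | 22% |
| 20% | 22 | <0.1% | <0.1% |

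**3. Can the model be fitted?** Protocol Table 1 schedules serum chemistry at 8 post-baseline visits: 3–4 h, 5–6 h, 8–10 h, and Days 2, 3, 7, 14 and 28. SAP 8.2.7 names an MMRM without a covariance structure; I take the unstructured form in SAP 8.2.1 to apply.

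- Covariance parameters: 8 × 9/2 = 36.
- Fixed effects: 6 (intercept, treatment, baseline SSS, baseline creatinine, age group, neurotoxicity) + 7 (visit) + 7 (visit by treatment) = 20.
- Total: 56 parameters. Five patients supply at most 5 × 8 = 40 observations; eleven supply at most 88.

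With 8 or fewer patients, an unstructured 8 × 8 covariance matrix cannot be estimated once arm means are fitted at each visit. With 11 it is marginal at best.

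**4. Illustrative power.** This borrows the primary endpoint's standardized effect, 1.1/1.75 = 0.629, because none is given for creatinine. A two-group t-test has power of about 9% at 3 per arm (f = 5%, rounded), 17% at 6 per arm (f = 10%) and 29% at 11 per arm (f = 20%).

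**5. Cases left out.** If f = 5% and 10% of the remaining patients develop renal injury (both assumed), 110 × 0.95 × 0.10 ≈ 10 new cases fall outside the model, against 5.5 baseline cases inside it.

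**6. Where new-onset injury is still compared between arms.**

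| Injury | Marker-specific model | Other inferential analysis | Descriptive only |
|---|---|---|---|
| Renal | Excluded | Primary endpoint, SSS-AUC to Day 7, complete SSS to Day 7, 6/9-hour subscore | Creatinine summaries to Day 28, shift tables, Acute Kidney Injury FMQ |
| Coagulation | Excluded | Same, through the hematologic section | By-arm figures, laboratory summaries |
| CK | Excluded | None | By-arm summaries and figure |
| Free hemoglobin | Excluded | None; LDH and haptoglobin unspecified | By-arm summaries and figure |

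The renal section is a diluted route. It carries at most 3 of the 20 points in SSS-AUC (3 + 3 + 4 + 4 + 3 + 3), and SAP 8.1.2.1 makes the subscore AUCs descriptive.

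**The case against.** The strongest reply is that new injury is already covered, and much of it stands. A reader might infer from the four restrictions that injury arising after enrolment is never tested, or that 8.2.7 is the only comparative kidney analysis. Neither holds. The renal and hematologic sections are scored in every ITT patient and enter the primary endpoint, SSS-AUC and the complete SSS. Appendix B scores creatinine against the patient's own baseline, so the Day 3 renal failure case does raise a tested SSS-AUC.

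A reader might also infer that excluded patients contribute nothing, or that renal harm would go unseen. The documents do not support this either. Sections 8.2.5 and 8.2.7 begin with by-arm descriptive summaries. SAP Table 6 plans ITT figures for CK, free hemoglobin and coagulation. Protocol 11.1.1 makes clinically significant worsening of renal tests an adverse event, and SAP 9.1.3 and 9.3 report the Acute Kidney Injury FMQ and shift tables by arm. These carry no inferential test (SAP section 9), and the shift tables use the normal range, not the efficacy thresholds.

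Three further points count for the plan:

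- Studying resolution in affected patients fits the secondary objective in SAP 2.1, and a restriction on baseline values does not bias the randomized comparison.
- Protocol 13.1.4.5 says only that ANCOVA or MMRM will be considered, so it never promised a full-ITT model for each marker.
- SAP 8.2 and 8.2.1 allow simpler covariance structures, fewer covariates or other estimation routines.

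The fallbacks do not answer the point, because none of them widens the population. Sections 8.2.9, 8.2.10 and 8.2.12 each have a rule for fewer than five patients or events; 8.2.7 has none.

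**Conclusion.** The point holds in limited form. The four marker-specific models use a narrower population than Protocol 13.1.4.5 and SAP section 5 state, and they cannot test prevention of new injury. For CK and free hemoglobin, new-onset elevation has no clear inferential test anywhere in the plan. For kidney and coagulation, the gap is in the marker-specific analysis: new injury is tested within composites through Day 7 and in the subscore analyses, which I read as 6/9-hour analyses because SAP 8.1.1 places them under the primary endpoint. After Day 7 new renal injury is only described, although the kidney endpoint runs to Day 28.

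That the kidney subset is small is an inference from the eligibility rules, not a documented fact. At an assumed 5 to 10% it is about 5 to 11 of 110 patients, and the unstructured model would then probably fail. At 20% it would be about 22 and could be workable. The documents also give no basis for sizing the CK, hemolysis or coagulation subsets.

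The endpoints are exploratory and new renal injury is described in safety reporting, so the impact is moderate. The change is worth making but does not affect the primary conclusion.

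**What to change.** In SAP 8.2.3, 8.2.4, 8.2.5 and 8.2.7:

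1. Run the model in all ITT patients with the baseline value of the marker as covariate. For coagulation, add the baseline category of the test concerned, which 8.2.3 does not list.
2. Keep the baseline-abnormal subset as a supportive analysis of resolution.
3. Tabulate by arm the patients below the threshold at baseline who newly cross that same threshold afterwards.
4. Add a minimum-count rule for the subset, with descriptive reporting below it, as in 8.2.9 and 8.2.10.
5. State the method and population for LDH and haptoglobin, make the title of Table 14.2.9.1 match its population, and record the change in section 10.

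The cost is SAP wording and a few tables from data already collected. The downside is that patients who stay normal dilute the mean effect; the retained subset addresses that.
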